9. DATA HANDLING CONVENTIONS

This section describes data handling conventions including the study periods, handling of premature withdrawal and missing data and derived and transformed data.

9.1. Study Periods

The study has a Treatment Period (to Week 52) and a Post Treatment Follow-up (Years 2 through 5) as described below. Summaries of data collected during the latter will be defined in more detail in a separate RAP.

9.1.1. Treatment Period (to Week 52)

Subjects will receive IP through Week 48 with a final treatment period in clinic visit conducted at Week 52. Subjects who discontinue IP prior to Week 48 will have a follow-up in clinic visit performed approximately 4 weeks after the last dose of IP.

Per protocol, subjects may withdraw from IP during Year 1 and continue on study, or may withdraw from Year 1 study visits and consent to a Week 52 follow up. As a result, the time ‘on treatment’ versus the time ‘on study’ will differ for some subjects. Therefore, 2 analysis periods have been defined as the ‘On-Treatment’ and ‘On-Study’ periods. Further detail below.

The primary analysis summaries of Mortality, AESIs and SAEs will be performed using the ‘On-Treatment’ Period (defined in the table below).

Supportive summaries of the primary analysis will be performed using the ‘On-Study’ Period (includes on and off treatment data to Week 52).

For subjects who withdraw and re consent for a Week 52 assessment only mortality and malignancy are assessed at Week 52, whereas all other endpoints will be assessed only up until the time of withdrawal. Therefore, in this case follow-up for mortality and malignancy will be longer than for other assessments.

Study Period	Definition
Pre-Treatment	Date < Study Treatment Start Date
On-Study to Week 52	
All data except Mortality and Malignancy events:
 
Study Treatment Start Date ≤ Date ≤ minimum (Date of Death, maximum (Study Withdrawal or Completion Date (DSSTDT), Study Treatment Stop Date + 28 Days))
 
Mortality and all Malignancy events including NMSC (see Section 9.5.12 for definitions of mortality and malignancy events):
 
 • Alive or Lost to Follow Up at Week 52 Follow-Up: Study Treatment Start Date ≤ Date ≤ minimum (Last Known to be Alive Date, Study Treatment Start date + 371) • Dead at Week 52 Follow-Up: Study Treatment Start Date ≤ Date ≤ Date of Death • Week 52 follow-up missing: Study Treatment Start Date ≤ Date ≤ minimum (Date of Death, maximum (Study Withdrawal or Completion Date (DSSTDT), Study Treatment Stop Date + 28 Days)) 
Note: If the derived on-treatment period (i.e. study treatment stop date + 28 days) ends later than the derived on-study to Week 52 period, the derived on-study period will be updated such that it ends in line with the derived on-treatment period.

On-Treatment	
All data:
 
 • Study Treatment Start Date ≤ Date ≤ minimum (Date of Death, Study Treatment Stop Date + 28 days)

Note: After study withdrawal or last exposure plus 28 days (whichever occurs later) if AESIs and SAEs are recorded, other than mortality and malignancy, these will not be included in the on-study period. See Section 11.2.1 for further detail on how these events will be handled.

Note: For mortality, date of death will be derived as the end date of the SAE with fatal outcome.

Note: Each study treatment infusion should have a start date and end date recorded, but in some cases only one variable is completed. The study treatment stop date is the date of the final study treatment infusion (taken as the first non-missing date of the final study treatment infusion start or end date).

Note: Only dates will be used to identify start and end of treatment (times will not be considered).

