6.3 Treatment Period

Subjects will be evaluated at the study site for the scheduled study visits outlined in the Study Calendar (Table 6-1). On Day 0, the subject will be randomized and receive the first dose of study agent. Subjects will be dosed at Week 2, Week 4 and approximately every 28 days (calculated from the Day 0 dose) thereafter through Week 48. The final treatment period evaluation for the study will occur at Week 52. Time windows are defined as ± 3 days for visits at Week 2 and Week 4, and ± 7 days for visits from Week 8 through Week 52. All study visits should occur within the visit window of the scheduled study visit. In rare circumstances, when the scheduled visit cannot be done within the visit window the Medical Monitor may be contacted for advice. Similarly, while all assessments for a dosing visit should be performed same day, in rare circumstances, an investigator may be permitted to conduct the assessments over two consecutive days so long as the infusion of the study agent is performed on the second day and after all other assessments.

All subjects who do not withdraw consent to participate in the first year monthly study visits and regardless of whether they continue to receive study agent will be followed on-study through Week 52 and annually for Years 2 through 5 (Week 260). All subjects will have a follow-up visit performed approximately 4 weeks after the last dose of study agent. In the event that a subject withdraws consent to participate in the first year monthly study visits, an attempt should be made at the time of consent withdrawal to obtain consent to contact the subject at Week 52 and annually for Years 2 through 5 (Week 260) to assess mortality and malignancy (including NMSC).

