6.6 Withdrawal from Study

Subjects will be free to withdraw from the study at any time, for any reason. It is understood by all concerned that an excessive rate of withdrawals can render the study uninterpretable; therefore, unnecessary withdrawal of subjects from study should be avoided.

If a subject withdraws consent to participate in the first year monthly study visits, at the time of consent withdrawal it is requested that the site attempt to obtain consent to contact the subject at Week 52 and annually for Years 2 through 5 (Week 260) to assess mortality and malignancy (including NMSC).

Table 6-1 Study Calendar

Study Week	Screening visit (within 30 days of Day 0 visit)	Day 0 visit	Wk 2 visit (Day 14 ± 3 d)	Wk 4 visit (Day 28 ± 3 d)	Wk 8 visit (Day 56 ± 7 d)	Wk 12 visit (Day 84 ± 7 d)	Wk 16 visit (Day 112 ± 7 d)	Wk 20 visit (Day 140 ± 7 d)	Wk 24 visit (Day 168 ± 7 d)	Wk 28 visit (Day 196 ± 7 d)	Wk 32 visit (Day 224 ± 7 d)	Wk 36 visit (Day 252 ± 7 d)	Wk 40 visit (Day 280 ± 7 d)	Wk 44 visit (Day 308 ± 7 d)	Wk 48 visit (Day 336 ± 7 d)	Wk 52 visit (Day 364 ± 7 d)	Annual Follow-up Years 2-5 ¹¹
Written Informed Consent, Demographics, Medical History, SLE History/Diagnosis, Eligibility Criteria	x																
SELENA SLEDAI (related laboratory tests within 30 days prior to screening date)	x																
Pregnancy test ¹	x	x	x	x	x	x	x	x	x	x	x	x	x	x	x	x	
Weight ²		x	x	x	x	x	x	x	x	x	x	x	x	x	x	x	
Baseline/screening suicidality assessment (C-SSRS Appendix 4)	x																
Since last visit suicidality assessment (C-SSRS Appendix 5) ³		x	x	x	x	x	x	x	x	x	x	x	x	x	x	x	
Study Agent Administration ⁴		x	x	x	x	x	x	x	x	x	x	x	x	x	x		
Record Concurrent Medications used to treat SLE	x	x	x	x	x	x	x	x	x	x	x	x	x	x	x	x	
Assess/Record Serious Adverse Events ⁵		x	x	x	x	x	x	x	x	x	x	x	x	x	x	x	
Assess/Record all Opportunistic Infections and Other Infections of Interest (including TB reactivation) ⁶		x	x	x	x	x	x	x	x	x	x	x	x	x	x	x	
Assess/Record all Malignancies (including NMSC)		x	x	x	x	x	x	x	x	x	x	x	x	x	x	x	x
Assess/Record Serious Infusion and Hypersensitivity Reactions		x	x	x	x	x	x	x	x	x	x	x	x	x	x		
Record Hospitalizations ⁷		x	x	x	x	x	x	x	x	x	x	x	x	x	x	x	
Pharmacogenetic Sampling (consenting subjects only) ⁸		x															
SLICC/ACR Damage Index ⁹		x															X ⁹
Survival Assessment ¹⁰																x	x

Footnotes for the study calendar appear on the following page.

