7.4 Suicidality Assessment

Some autoimmune diseases have an increased risk of suicidal behavior and/or ideation ([Bachen, 2009](#); [Timonen, 2003](#); [Stenager, 1992](#)). In order to objectively assess suicidality in belimumab clinical programs the C-SSRS ([Appendix 4](#) and [Appendix 5](#)) will be utilized to collect information on suicidal behavior and ideation. ‘Baseline’ C-SSRS ([Appendix 4](#)) will be used at screening ONLY; whereas, ‘Since Last Visit’ C-SSRS ([Appendix 5](#)) will be used at all other designated study visits. SLE patients have an increased prevalence of mood and anxiety disorders compared with the general population and disease activity may contribute to this higher risk. The incidence of major depressive disorder (MDD) among SLE patients has been reported to be as high as 47% ([Bachen, 2009](#)). Since active SLE and MDD may increase the risk of suicidal ideation or behavior before or during clinical studies, subjects participating in this study will be assessed for suicidality at every visit.

Subjects who answer “yes” to any suicidal behavior or “yes” to suicidal ideation questions 4 or 5 on the C-SSRS should be referred to appropriate psychiatric care and prompts the completion of a SAE worksheet. The medical monitor should be notified when these events occur. In addition, a “yes” to any suicidal behavior or “yes” to suicidal ideation questions 3, 4, or 5 on the C-SSRS prompts the completion of a Possible Suicidality Related History Questionnaire (PSRHQ) eCRF (PSRHQ, only the first time this condition is met), and a Possible Suicidality Related Questionnaire (PSRQ) eCRF at all times this condition is met.

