9.5.15. Treatment-Emergent C-SSRS

For suicidal ideation, the pre-treatment reference period is the lifetime history, current history and baseline (for further detail refer to the IDSL documentation). For suicidal behavior, the pre-treatment reference period is the lifetime history and baseline (note: suicidal behavior is not re-assessed for the current history time period).

Suicidal ideation and suicidal behavior will be considered as distinct categories and assessed independently of each other. Treatment emergence will be assessed for the on-treatment period and the on-study period.

Suicidal ideation will be assessed using responses to C-SSRS ideation questions (categories 1 to 5) only. Suicidal behavior will be assessed using responses to C-SSRS behavior questions (categories 6 to 10) only.

- **Treatment emergent suicidal ideation** will be assessed using the maximum ideation score pre-treatment, compared to the maximum ideation score post-treatment (on-treatment or on-study as appropriate). If the maximum ideation score worsens relative to the pre-treatment reference period then this will be considered a treatment emergent suicidal ideation. This is derived from responses to suicidal ideation questions (categories 1 to 5).
- **Treatment emergent suicidal behavior** will be assessed using the maximum behavior score pre-treatment, compared to the maximum behavior score post-treatment (on-treatment or on-study as appropriate). If the maximum behavior score worsens relative to the pre-treatment reference period then this will be considered a treatment emergent suicidal behavior. This is derived from responses to suicidal behavior questions (categories 6 to 10).
- **Treatment emergent suicidal ideation or behavior** will be defined as a subject having a treatment emergent suicidal ideation (as defined above) and/or a treatment emergent suicidal behavior (as defined above). This definition is used to assess the protocol defined AESI endpoint of ‘Suicidality (C-SSRS)’ (see Section 9.5.15).

Suicidal Ideation (categories):

1. Wish to be Dead
2. Non-Specific Active Suicidal Thoughts
3. Active Suicidal Ideation with Any Methods (Not Plan) without Intent to Act
4. Active Suicidal Ideation with Some Intent to Act, Without Specific Plan
5. Active Suicidal Ideation with Specific Plan and Intent

Suicidal Behavior (categories):

6. Preparatory Acts or Behavior
7. Aborted Attempt
8. Interrupted Attempt
9. Non-Fatal Actual Suicide Attempt
10. Completed Suicide

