11.1.2. Protocol-Defined AESI

Protocol-defined AESIs are defined in Section [9.5.12](#).

Note, for Suicidality (C-SSRS) only, a subject must have at least one pre-treatment C-SSRS assessment (screening and/or baseline) and at least one on-treatment C-SSRS assessment (post-baseline) to be included in the summaries.

Percentages

For each of the AESIs a summary of the number and percentage of subjects experiencing at least one event will be provided for belimumab and placebo as well as the difference in the percentage of subjects (and 95% CI) between the belimumab and placebo groups using the same methodology as for mortality.

Subject Incidence Rate

The incidence rate for each AESI per 100 subject years will be provided for belimumab and placebo groups as well as the difference between placebo and belimumab (and 95% CI) using the same methodology as for mortality.

Event Incidence Rate

The number of events and event rate for each AESI, except Suicidality (C-SSRS), per 100 subject years will be provided for belimumab and placebo groups.

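### The last-infusion + 28 days cut-off can drop the C-SSRS covering the final dosing interval from the primary on-treatment suicidality endpoint

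*SAP*

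**What the plan says.** The Week 52 RAP, Section 9.1.1, sets one on-treatment period for all data: "Study Treatment Start Date ≤ Date ≤ minimum (Date of Death, Study Treatment Stop Date + 28 days". The same section fixes the end point: "The study treatment stop date is the date of the final study treatment infusion". Section 11.1 makes this period the primary interest and the on-study period an important supportive one.

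Suicidality (C-SSRS) is a protocol-defined AESI. Section 9.5.15 derives treatment-emergent ideation and behaviour from maximum scores. For behaviour, the pre-treatment maximum is "compared to the maximum behavior score post-treatment (on-treatment or on-study as appropriate"; the ideation rule has the same form. No C-SSRS-specific date or window is given.

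On collection, Protocol Section 7.4 reserves the baseline form for screening and says of the other form: "Since Last Visit’ C-SSRS ([Appendix 5](#)) will be used at all other designated study visits". A footnote to Table 6-1 requires it before the infusion. What happens after a dose is therefore recorded at the next visit. Under Protocol Section 6.5 that is Week 52 for those who complete dosing, and the next scheduled visit for those who stop early.

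On timing, Protocol Section 6.3 counts visits from the Day 0 dose, and its windows, which run to the Week 52 visit, are as follows: "Time windows are defined as ± 3 days for visits at Week 2 and Week 4, and ± 7 days for visits from Week 8 through Week". Table 6-1 gives "Wk 48 visit (Day 336 ± 7 d") and "Wk 52 visit (Day 364 ± 7 d").

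**The concern.** An SAE carries its own event date, so a cut-off at last dose + 28 days places it sensibly. A C-SSRS response has only a visit date but describes the whole interval since the previous visit. With the cut-off set exactly on the nominal spacing and no tolerance, a visit one day beyond 28 days takes the whole assessment out of the on-treatment period, although 28 of the 29 days it describes lie inside that period.

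The affected interval is the one in which a subject stops study agent, possibly because of the event. Under Section 9.5.4 those 28 days remain in on-treatment subject-years while their only assessment is discarded. Because the endpoint uses a maximum score, removing an assessment can only lower it. The on-treatment percentage and rate can therefore only move down. The double dotplots and subgroup repeats in Section 11.1 are specified for the on-treatment period only, so they would carry the same loss.

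**Working it through.** **Inputs.** The cut-off is the last infusion + 28 days (RAP 9.1.1). Week 48 is Day 336 ± 7 and Week 52 is Day 364 ± 7 (Protocol Table 6-1). Weeks 2 and 4 have ±3 days and Week 8 onward ±7 days (Protocol 6.3). All are anchored to Day 0, so a shifted dose does not move the next visit.

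**The plan's own spacing.** 364 − 336 = 28 days, equal to the cut-off.

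**Allowed gap.** Let d be the deviation of the last dosing visit and e that of the next visit. Then gap = nominal spacing + e − d.

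| Last dose → next visit | Nominal | Allowed range | Can exceed 28? |
|---|---|---|---|
| Day 0 → Week 2 | 14 | 11 to 17 | No |
| Week 2 → Week 4 | 14 | 8 to 20 | No |
| Week 4 → Week 8 | 28 | 18 to 38 | Yes |
| Week 8 or later → next | 28 | 14 to 42 | Yes |

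**Trigger.** With nominal spacing 28, the assessment is excluded when 28 + e − d > 28, that is, when e > d. What matters is the gap since the infusion, not lateness against the calendar. A Week 52 visit 5 days late after a Week 48 dose 5 days late is kept. An on-time Week 52 visit after an early Week 48 dose is excluded.

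**Share of final assessments excluded.** The documents give no visit-timing data, so this is a range:
- Every visit exactly 28 days after the last dose: 0%.
- Independent, uniform deviations over ±7 days (assumption): 15 × 15 = 225 pairs, 15 of them ties, so (225 − 15)/2 = 105 have e > d, and 105/225 = 46.7%.
- The same assumption over ±3 days: (49 − 7)/2 = 21, and 21/49 = 42.9%.

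**Share of on-treatment recall time lost, completers.** The final interval is 28/364 = 7.7% of the time and 1 of 14 post-baseline assessments. Multiply by the share of subjects affected:
- 10% affected: 0.8%
- 25% affected: 1.9%
- 46.7% affected: 3.6%
- all affected (outer bound): 7.7%

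**Early stoppers.** For a last dose at Week 4, the assessments are Weeks 2, 4 and 8. If Week 8 falls more than 28 days after the dose, 1 of 3 assessments and 28/(28 + 28) = 50% of on-treatment recall time are lost for that subject.

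**Is there a rule elsewhere that prevents this?** The visit windows in RAP 9.5.3 are listed for withdrawal and mortality summaries only. For mortality and malignancy, the on-study end in 9.1.1 does allow for the Week 52 window (treatment start + 371 days). No such allowance is given for the C-SSRS.

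**The case against.** A single last-dose + 28 days rule for all data is a coherent convention, and much can be said against making more of this.

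- *The assessment is lost to the trial.* A reader might infer this, but the documents do not support it. For non-mortality data, the on-study period in 9.1.1 runs to the later of study completion or withdrawal and last dose + 28 days. The record stays in the on-study AESI table, which is a headline output (Table 2.06).
- *Suicidal behaviour in the last interval goes unreported.* Also not supported. Under Protocol 7.4, any behaviour or ideation 4-5 prompts an SAE worksheet. Such events would be expected, by event date, in the on-treatment suicide/self-injury summaries (RAP 11.2.4). They would be missing only from the C-SSRS-defined endpoint. Ideation 1-3 has no such route.
- *Subjects who stop after one or two infusions are hit hardest.* Not so: their next visit is at most 20 days after the dose and is kept if attended.
- *The treatment comparison is distorted.* Nothing in the documents shows a difference between arms in the timing of final visits.
- *The governing date is not stated.* This objection stands. Use of the assessment date is read from the general date rule in 9.1.1. Section 9.5.15 refers to IDSL documentation that is not among the documents.
- *The 47% is driven by an assumption.* This stands too. Protocol 6.5 describes the follow-up visit as about four weeks after the last dose, and sites that schedule from the actual dose would bring the share towards zero.

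These points limit the size and reach of the problem. They do not remove it from the primary analysis.

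**Conclusion.** The point holds in limited form. If the C-SSRS is placed by assessment date, the stated rule excludes a protocol-compliant assessment of the final dosing interval from the primary on-treatment suicidality endpoint whenever the visit falls more than 28 days after the last infusion. It applies to last doses from Week 4 onward. The percentage and rate are biased slightly low, mainly for ideation 1-3. For completers the loss is between nil and about 3.6% of on-treatment recall time, the upper figure resting on independent, uniform in-window deviations. If events are spread evenly over time and both arms are affected alike, both rates and their difference shrink by about the same proportion. An effect that differs by arm would need final-visit timing to differ by arm, which the documents cannot show.

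A minor related inconsistency concerns who enters the on-study C-SSRS summaries. RAP 11.1.2 requires "at least one on-treatment C-SSRS assessment (post-baseline) to be included in the summaries", and 9.5.15 and 11.2.5.2 carry the same condition, whereas 11.2.5.3 asks for an on-study assessment. Very few subjects can be affected: someone with a single dose who missed Week 2 and whose next C-SSRS came after day 28.

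**What to change.** In RAP 9.1.1 and 9.5.15, state which date places a C-SSRS in a period. Add that the first look-back C-SSRS after the last infusion counts as on-treatment if dated no later than study treatment stop date + 42 days (28 + 7 + 7). This recovers every in-window final assessment. A limit of + 35 days would still miss 28 of 225 day pairs (12.4%) under the uniform assumption.

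The introduction to the Years 2 to 5 RAP says the Week 52 results have been unblinded and reported. If those outputs are final, the practical form is a sensitivity version of the on-treatment suicidality summary, labelled as added afterwards, with the number of assessments reclassified in each arm.

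Separately, align the on-study inclusion condition in 9.5.15, 11.1.2 and 11.2.5.2 with 11.2.5.3.

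The cost is two sentences and one derivation flag. The downside is that up to 14 days of off-treatment recall count as on-treatment, with no matching addition to subject-years.

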9.1.2. Post-Treatment Follow-Up

After the Treatment Period (to Week 52) all subjects will be contacted annually through Year 5 (Week 260) to assess mortality and malignancy (including NMSC). Annual follow-up also applies to subjects who discontinue IP before Week 48 and have remained in monthly follow-up and to subjects who withdraw consent from the study prior to Week 52 but re-consent for this annual follow-up. c

9.2. GSK Adjudication of Death Categories and AESI

See [Appendix 6: PSAP Sections for AESI Reporting](#) for sections of the PSAP relating to death categories and AESI adjudication.

All fatalities (reported during the Week 52 study period) will be identified in the clinical database and subsequently adjudicated by the GSK SRT into a general category of death.

AESI are identified per the preferred terms and other criteria described in [Appendix 6: PSAP Sections for AESI Reporting](#). Malignancies, serious post-infusion systemic reactions, potential opportunistic infections, suicidality and fatalities are adjudicated at the subject level by the GSK SRT. The adjudication occurs prior to database release and is performed for reporting purposes. Final confirmation of adjudications is required before database freeze (DBF).

9.3. Hospitalizations Review

A specific subject hospitalization form was not generated in the eCRF system for this study. Therefore, to measure all hospitalizations in this study, a manual clinical review process to identify the number of hospitalization events through review of all the SAEs has been implemented. The basis of this approach is that any event resulting in hospitalization mandates reporting as a SAE (refer to protocol Section 7.1).

Main review

The spreadsheet containing hospitalization data will be reviewed and updated in-stream and will be available for reporting. The summary of the process is presented below:

1. Clinical Programming will extract all SAEs from the eCRF into a spreadsheet listing for clinical review. Updates of SAE data will be extracted into the spreadsheet approximately every 4-6 weeks.
2. SAEs are reviewed by the study clinical investigation lead (CIL) and medical monitor (MM), or their equivalent designees. The reviewer determines the number of hospitalizations, and then assigns a hospitalization code for each hospitalization identified. The code consists of a combination of the Subject ID number and the hospitalization number for that subject (e.g., hospitalization code **PPD** = Subject ID **P** and hospitalization **PP**).
3. In the absence of a 'reason for hospitalization' data field in the eCRF, to avoid the potential bias and/or influence of the Sponsor (GSK) in the determination of reason for hospitalization in any way, the SAE source verbatim term will be reported in the

listing of hospitalizations and indicated as ‘SAE(s) contributing to Hospitalization’. If more than one SAE is reported within the same hospitalization, all SAE source verbatim terms will be reported on the listing.

4. Once there are no outstanding issues after review of each SAE case (either after initial review, or after resolution of any queries), the review is then documented in the spreadsheet as completed with an initial and date by the reviewer. The spreadsheet is then reflected back into the ADaM datasets by Clinical Programming for reporting.

At any time, any SAEs from individual reviewers can be flagged for further team discussion / review to occur during ad hoc roundtable SAE review meetings, or by consult with the MM.

Independent secondary review

In addition, a second independent review of the SAEs for the hospitalization events will be performed by an independent medical reviewer. The reviewer will be provided with the guidelines for review based on the protocol and following the same convention of the main review described above.

Once the review is completed, a comparison between the main review and the independent secondary review spreadsheets will be performed for the number of hospitalization and the assigned hospitalization code where applicable. Identified discrepancies will be discussed and reconciled at a round table meeting between the GSK clinical representatives (MM and study CIL or designee) and the independent medical reviewer. The reconciled records will be reflected on the main spreadsheet following the round table review meeting.

Full details of the hospitalizations review process will be documented as part of the Study Data Quality Plan and associated documents.

